3.4.2 Immunogenicity (IM) Analysis

Immunogenicity (IM) analyses will be conducted in Safety Set.

Samples collected for IM assessment at selected time points will be analyzed for anti-volanesorsen antibodies (i.e., anti-drug antibodies; ADA). Samples will be designated 'IM positive' based on both positive screening and confirmation assay results (i.e., confirmed positive result), and otherwise be deemed 'IM negative'. Study subjects will be given 'positive' subject IM status if they have at least one confirmed positive sample at any time during the treatment or post-treatment evaluation periods. Study subjects will be given 'negative' subject IM status if all evaluated IM sample results during the treatment and post-treatment evaluation periods are negative and they have at least one evaluable IM result post dose. Otherwise, study subjects will be given 'unknown' subject IM status.

Sample IM status (screen positive/negative, confirmed positive/negative or not evaluable, and when applicable, titer of anti-volanesorsen antibodies) before, during, and after treatment with Study Drug (volanesorsen or placebo) will be listed for Group 1 and Group 2 patients by their prior treatment in Study ISIS 304801-CS6 and ISIS 304801-CS16 and newly enrolled patients as a separate group (Group 3) by study day. Subject IM status (positive/negative or unknown) for all evaluable patients, along with the study day associated with the first positive IM status emerged (T_{first} , i.e., onset of ADA development), the last positive IM status observed (T_{last}) and max and/or end of treatment titer will be listed by treatment and dose.

Additionally, the sample and patient IM incidence (number) and incidence rate (percent) will be summarized as the total number and percent of evaluated patients with antibody negative, positive, and unknown status by the group presented in [Section 3.2.1](#). Furthermore, onset, and peak titer of the ADA response, if applicable, will be summarized as median, interquartile range (25th percentile, 75th percentile), and range (minimum, maximum).

Potential relationships between immunogenicity results (e.g., IM status) and selected efficacy (e.g., % change in fasting TG from baseline at 3-, 6-, and 12-month endpoints), safety, and pharmacokinetic measures will be evaluated in an exploratory manner.

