3.4 Pharmacokinetic and Immunogenicity Analysis

PK concentration and Immunogenicity (IM) results obtained in the open-label study will be summarized along with those from the index study. Patient data listings will also be provided.

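### Antibody incidence and onset are not referenced to a pre-volanesorsen result, so patients with persistent pre-existing positivity are reported as having developed antibodies on drug

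*SAP*

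**What the plan says.** In SAP Section 3.4.2 a sample is positive when both the screening and the confirmation assay are positive. A patient is positive with "at least one confirmed positive sample at any time during the treatment or post-treatment evaluation periods". A patient is negative when every evaluated sample in those periods is negative and "they have at least one evaluable IM result post dose". All others are unknown.

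The summary is described as incidence and incidence rate, and consists of the "total number and percent of evaluated patients with antibody negative, positive, and unknown status". The study day of the first positive is labelled "onset of ADA development" and is summarised by median, quartiles and range.

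Pre-treatment samples appear in one place: sample status and, where applicable, titer "before, during, and after treatment with Study Drug (volanesorsen or placebo) will be listed". Section 3.4 adds that "PK concentration and Immunogenicity (IM) results obtained in the open-label study will be summarized along with those from the index study".

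**The concern.** Incidence and onset both assert that something began after exposure. The rule in Section 3.4.2 cannot support that, because it never asks whether the patient was already positive. The reported figure is the share ever positive in the counted periods, which is a period prevalence.

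Three results are affected: the reported antibody rate, the onset distribution, and every analysis that reuses IM status. The last group comprises the stratified plasma concentrations in Section 3.4.1.1, the stratified PK parameters in Section 3.4.1.2, and the exploratory relations with efficacy, safety and PK in Section 3.4.2. In each, patients whose reactivity predates the drug are pooled with those who responded to it.

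**Working it through.** The SAP states no antibody rate, so there is no planned figure to reproduce. The check applies the rule to patient patterns and then illustrates its size.

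**Does another section repair the rule?** Section 3.2.3 defines baselines for lipids, quality of life, abdominal pain, platelets, ECG, vital signs, safety laboratory data and MRI, but none for IM. Section 3.5 defines Day 1 of Volanesorsen and limits the definition to that section; 3.4.2 does not use it. Section 3.5.2.1 shows that the authors apply the needed logic elsewhere: for linked records, an adverse event present before the first volanesorsen dose and not worse or newly serious afterwards is not treatment-emergent. IM has no counterpart.

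**Patterns under the rule**

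| Pattern | Classed positive? |
|---|---|
| Positive before volanesorsen, still positive afterwards | Yes, with onset at the first counted positive day |
| Positive on index placebo, still positive in CS7 | Yes, on any reading |
| Positive only on index placebo | Yes if the treatment period includes the index study; no if it means CS7 alone |
| Positive only before treatment, negative at every later sample | No |

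No pattern is removed or relabelled because of a positive pre-volanesorsen result.

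**Size (illustration).** Inputs: N = 70, from the approximate maximum in Section 1.1, all taken as evaluable; p, the share with pre-existing positivity that persists; and t, the true emergent rate among baseline-negative patients. Both p and t are assumptions.

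- Rate under the SAP rule: p + (1-p)t.
- Excess over t: p + (1-p)t - t = p(1-t).
- Chance of at least one such patient: 1 - (1-p)^70.
- Share of positives that are pre-existing: p / [p + (1-p)t].

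With t = 20%:

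| p | Expected patients (70p) | Chance of at least one | SAP rate | Excess | Pre-existing share of positives |
|---|---|---|---|---|---|
| 1% | 0.7 | 0.505 | 20.8% | 0.8 points | 4.8% |
| 3% | 2.1 | 0.881 | 22.4% | 2.4 points | 13.4% |
| 5% | 3.5 | 0.972 | 24.0% | 4.0 points | 20.8% |
| 10% | 7.0 | 0.999 | 28.0% | 8.0 points | 35.7% |

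At p = 5% the excess is 0.05 × 0.90 = 4.5 points for t = 10% and 0.05 × 0.70 = 3.5 points for t = 30%.

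The denominator matters. At p = 5% and t = 20%, emergent cases over all evaluated patients are 0.95 × 0.20 = 19%, and the gap to 24% is 5 points. Over baseline-negative patients the rate is 20% and the gap is 4 points.

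**Onset.** In the same example 20.8% of positives have a false onset. If those all fall before the genuine ones, the reported median is the (50 - 20.8)/(100 - 20.8) = 37th percentile of the genuine onsets.

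**The case against.** The study has no formal hypothesis (Section 1.3), is evaluated by summary tables (Section 3.1), and treats the relations of IM status with outcomes as exploratory. No decision depends on the antibody rate. Sample-level results before, during and after treatment are listed, so a reader could find pre-existing positives patient by patient. All of this stands, and it limits the consequence. It does not correct the summary tables, whose labels say something that their rule does not measure.

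A reader might also infer more than the documents support:

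- *That everyone positive before the first dose is counted.* The rule looks only at the treatment and post-treatment periods, so a patient who is positive beforehand and negative at every later sample is not counted.
- *That a positive seen only on index placebo makes a patient positive.* The mention of placebo as Study Drug stands in the sentence about listings, not in the status rule, and Section 2 uses the same period names for CS7 itself. Against that, Section 3.4 summarises index IM results with the open-label ones, and 3.4.2 does not say whether the treatment period includes the index study. This is an ambiguity, not an established error.
- *That the Treatment naive group is worst affected.* This is not shown. If index data are included, the index-volanesorsen groups are also followed from their first dose.
- *That the size is known.* It is not. Every rate used above is assumed.

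**Conclusion.** The point holds in limited form. On every reading of Section 3.4.2, a patient positive before volanesorsen and still positive afterwards is reported as an incident case with a false onset, and enters the IM-positive stratum of the PK summaries. The handling of positives seen only on index placebo is left open.

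The excess in the reported rate is p(1-t) relative to a rate among baseline-negative patients: 0.8 to 8.0 points for p from 1% to 10% at t = 20%, and 4 points at p = 5%. This assumes that pre-existing positivity persists to a confirmed sample in the counted periods and that none of these patients has a boosted response that would count as drug-induced. The size cannot be fixed from the documents, but the mismatch between label and rule does not depend on it. The matter goes beyond missing detail, because it changes the rate, the onset distribution and the strata.

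**What to change.** Amend Section 3.4.2, with a matching entry in 3.2.3:

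1. Extend Day 1 of Volanesorsen to this section and define baseline IM status from samples taken before it. State the rule when several pre-dose results disagree.
2. State that index-placebo samples count as pre-volanesorsen.
3. Report three categories separately: pre-existing; treatment-emergent (baseline negative, then confirmed positive); and treatment-boosted (baseline positive with a titer rise fixed in advance). Without the boosted category, a genuine response in a baseline-positive patient would be lost.
4. State the denominator for each category, for example baseline-negative patients with an evaluable post-dose result for the emergent rate.
5. Give a rule for missing pre-dose samples. The shift tables in Section 3.5.4.2 already label a missing baseline as unknown, and the same could be done here.
6. Compute onset from Day 1 of Volanesorsen in treatment-emergent cases only.
7. Say which status defines the PK strata and the exploratory analyses.

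The cost is slightly more derivation work on results already due to be listed. The treatment-emergent rate may differ from the ever-positive rate, which can still be shown if it is called prevalence.

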3.5 Safety Analyses

Safety endpoints including treatment exposure, AEs, clinical safety lab, vital signs, physical examination, 12-lead ECG, Echocardiogram, prior and concomitant medication use, and MRIs will be summarized in Safety Set.

On-Study period (from **Day 1 of Volanesorsen** to end of the study) in the open-label study will be classified to 3 periods:

- On-treatment period: from the first dose of Volanesorsen to the last dose of Volanesorsen + 28 days
- After-treatment period: from the last dose of Study Drug + 29 days to the last dose of study medication + 90 days
- Post-follow up period: after the last dose of Study Drug + 90 days

For vital sign, clinical safety lab, or 12-lead ECG,

- Visits of summary tables include baseline and labeled post baseline visits in the open-label study.
- **Safety Baseline** is defined in the [section 3.2.3](#) of this SAP.

For AEs, prior and concomitant medication use, each summary table will present the open-label study data.

For treatment exposure, details are discussed in the [section 3.5.5](#) of this SAP.

By patient data listings will display data collected in the open-label study.

In this section, **Day 1 of Volanesorsen** is defined as the first day volanesorsen is administered to the patient. For patients on active treatment in the index study, Day 1 of Volanesorsen will be the first day volanesorsen is administered in the index study. For patients on placebo in the index study, Day 1 of Volanesorsen will be the first day volanesorsen is administered in this open-label study.

Patient profile figures will be generated for selected patients to provide graphical profile of endpoint of interest.

3.5.1 Imputation of Missing/Partial Dates

3.5.1.1 Adverse Events

For AEs, the following imputation rules will be applied to impute start dates under conservative principles:

- If year, month and day are all missing then assign **Day 1 of Volanesorsen**.
- If month and day are missing and year is
 - The same as the year of **Day 1 of Volanesorsen** then assign the month-day of first Study Drug.
 - Earlier than the year of **Day 1 of Volanesorsen** then assign December 31.
 - After the year of **Day 1 of Volanesorsen** then assign January 1.

If only day is missing and month-year is

- The same as the month-year of **Day 1 of Volanesorsen** then assign the day of first Study Drug.
- Earlier than the month-year of **Day 1 of Volanesorsen** then assign the last day of the month.
- After the month-year of **Day 1 of Volanesorsen** then assign the first day of the month.

Imputation will be performed only for the end date only if the day or month is missing (i.e. year is present) for a resolved AE as follows:

- If month and day are missing and year is
 - The same as the year of the last dose of Study Drug then assign the month-day of the last dose of Study Drug.
 - Otherwise, assign December 31.
- If only day is missing then assign the last day of the month.

If the imputed start date is later than the imputed end date then set the imputed start date to the imputed end date.

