Case 2c: Both AE records in the pair occur before first dosing on **Day 1 of Volanesorsen**.

Neither AE is counted as treatment-emergent.

When counting the total number of treatment-emergent events, events linked together through change in severity will still be counted as separate events.

TEAE will be classified into three periods: on-treatment, after-treatment, and post-follow up periods and are defined as follows based on (imputed) start date of the event.

The frequency of patients with any incidence of AEs and the number of events will be summarized by MedDRA preferred term and system organ class for:

1. Any TEAE, any on-treatment TEAE, any after-treatment TEAE.
2. TEAEs related to Study Drug. Related is defined as "Related", "Possible", or missing relationship to Study Drug.
3. Any treatment emergent adverse event by severity. At each level of patient summarization, a patient with multiple events is counted only once according to the worst reported severity. Adverse events with missing severity will be categorized as "Missing" for this summary.
4. TEAEs potentially related to Study Drug by severity.
5. Post-follow up adverse events
6. Serious TEAEs.
7. Serious on-treatment TEAE.
8. Serious TEAEs potentially related to Study Drug.
9. AEs leading to permanent treatment discontinuation, and
10. TEAEs leading to death.

Adverse event summaries will be presented alphabetically and by descending frequency of the percentage of patients in the overall column. An overview of AEs will be provided for all TEAEs, on-treatment TEAEs, and after-treatment AEs. Treatment-emergent AEs, treatment emergent SAEs, AEs that lead to treatment discontinuation, and TEAEs leading to death will be listed. Note that

imputed dates will be used for defining TEAEs and classification of TEAEs into on-treatment, after-treatment, and post-follow up periods. Originally reported dates will be used for listings.

On-study AEs will be also summarized by treatment and age for FCS patients and all patients in safety set.

Treatment emergent renal adverse events will be summarized.

In addition, an overview of adjudicated AEs will be provided for pancreatitis and MACE separately. Adjudicated events will also be listed.

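### A year-only AE end date in the year of last dose can pull a month-only, post-treatment start back into the on-treatment period

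*SAP*

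**What the plan says.** SAP section 3.5.1.1 imputes an AE end date "only if the day or month is missing (i.e. year is present) for a resolved AE as follows". When month and day are both missing there are two branches. If the end year is the year of last dose, the rule is "The same as the year of the last dose of Study Drug then assign the month-day of the last dose of Study Drug". For any other year it is "Otherwise, assign December 31".

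Start dates have their own rules. A start with a known month later than the month of first volanesorsen dosing, but no day, follows "then assign the first day of the month". A start with only a year, later than the year of first dosing, follows "then assign January 1".

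The section closes with a reconciliation rule: "If the imputed start date is later than the imputed end date then set the imputed start date to the imputed end date".

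These dates decide the period tables. Section 3.5.2.1 says that "imputed dates will be used for defining TEAEs and classification of TEAEs into on-treatment, after-treatment, and post-follow up periods". Section 3.5 defines the first period as "On-treatment period: from the first dose of Volanesorsen to the last dose of Volanesorsen + 28 days". The after-treatment period runs from day 29 to day 90 after last dose, and post-follow-up comes later.

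**The concern.** The last-dose branch of the end-date rule takes no account of when the AE began. If the AE is known to have started after the last dose, the imputed end falls before the start. The closing rule then resolves the conflict by moving the start, although the end is the date that was guessed. Section 3.5.1.1 contains nothing that keeps an imputed end on or after a start whose month was reported.

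At stake is the split of treatment-emergent AEs (TEAEs) between periods. Section 3.5.2.1 tabulates on-treatment and after-treatment TEAEs, post-follow-up AEs and serious on-treatment TEAEs. An event moved by this rule leaves a later-period table and enters an on-treatment one, although its reported month places it off drug.

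**Working it through.** The SAP states no figure on this point, so there is none to reproduce. The check applies the rules literally to assumed dates.

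**Inputs from the SAP**
- Imputed end, year-only, year of last dose: the last-dose date (3.5.1.1).
- Imputed end, year-only, any other year: 31 December (3.5.1.1).
- Start with the day missing, month after that of Day 1: first of the reported month (3.5.1.1).
- Reset: if start is later than end, start = end (3.5.1.1).
- Periods by start date: on-treatment to last dose + 28 days, after-treatment from + 29 to + 90, post-follow-up beyond (3.5).

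**Assumed dates:** Day 1 = 1 March 2016, last dose = 1 March 2017, AE resolved, end reported as 2017 only. The imputed end is then 1 March 2017. On-treatment ends on 29 March 2017 (+ 28) and after-treatment on 30 May 2017 (+ 90).

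| Reported start | Start before reset | Days after last dose | Period before reset | Start after reset | Period used |
|---|---|---|---|---|---|
| May 2017 | 1 May 2017 | 61 | after-treatment | 1 Mar 2017 | on-treatment |
| Jun 2017 | 1 Jun 2017 | 92 | post-follow-up | 1 Mar 2017 | on-treatment |
| 15 May 2017, reset covers complete dates | 15 May 2017 | 75 | after-treatment | 1 Mar 2017 | on-treatment |
| 15 May 2017, reset covers imputed starts only | 15 May 2017 | 75 | after-treatment | 15 May 2017 | after-treatment, but the end is 75 days before the start |
| 15 Mar 2017, reset covers complete dates | 15 Mar 2017 | 14 | on-treatment | 1 Mar 2017 | on-treatment |
| 2017 only | 1 Jan 2017 | before last dose | on-treatment | no reset | on-treatment |

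**Controls.** With the end reported as 2018, the imputed end is 31 December 2018 and the June 2017 start stays in post-follow-up. If 31 December is used for the 2017 end as well, as section 3.5.1.2 does for medications, the May start stays after-treatment and the June start stays post-follow-up. The fault therefore comes from the last-dose branch combined with the reset.

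**How general it is.** Take every last-dose day in one 365-day year, each later start day in that year, the start day missing and the end year-only:
- All pairs: 365 × 364 / 2 = 66,430.
- True start within 28 days of last dose: 9,814, on-treatment by definition.
- True start beyond 28 days: 66,430 − 9,814 = 56,616.
- Of these, already on-treatment before the reset because the first of the month falls early enough: 4,911.
- Moved into on-treatment by the reset: 56,616 − 4,911 = 51,705, and 51,705 / 56,616 = 91%.

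These pairs show how the rule behaves; they are not expected event counts.

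**Day 1 status.** The reset date is the last-dose date, which cannot precede Day 1. The event is on or after Day 1 both before and after the reset.

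**The case against.** The strongest reply is that the closing rule speaks of an imputed start, and a complete start is never imputed. Elsewhere, in section 3.5.2.1, the SAP puts the word imputed in brackets when it means either kind of date; the closing rule has no brackets. On that plain reading a fully dated off-drug AE keeps its start and its correct period, and only its imputed end is illogical. This stands. A reader might infer that any AE beginning after treatment, with a year-only end in the same year, is counted as on-treatment. The text does not support that: it is certain only for month-only starts, and starts in the first 28 days are on-treatment anyway.

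The conditions are also narrow. Section 2.5.1 describes edit checks for missing data and resolution of all queries before lock, which makes such records less likely. Tables of any TEAE, related TEAEs, severity, serious TEAEs and deaths do not depend on the period split, and listings show reported dates. All of this stands and limits the size.

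A reader might also call the end-date rule a breach of the SAP's conservative principles. Section 3.5.1.1 attaches that phrase to start dates only, so the charge does not hold in that form. Nor does the phrase excuse the reset. Leaning towards drug exposure is defensible for unknown components, but here a reported month is overridden and the event drops out of the later-period tables.

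Finally, the reset cannot simply be deleted. Suppose Day 1 is 20 March 2016, the start is reported as March 2016 and the end as 10 March 2016. The start is imputed to 20 March; only the reset returns it to 10 March, before treatment. Without it, a pre-treatment AE would count as a TEAE.

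**Conclusion.** The point holds as a minor defect. A wrong period follows with certainty when all of these apply: the AE is resolved; its end has only a year; that year is the year of last dose; its start has a month but no day; and the imputed start is beyond last dose + 28 days. For a complete start date after last dose, the SAP leaves two outcomes, both faulty: the reported start is overwritten, or the record ends before it starts.

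A reader might infer that the rule inflates the number of TEAEs. It does not change an event's status against Day 1; it changes which period the event is counted in.

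The number of affected records is unknown and probably small. With about 70 patients (section 1.1), one moved patient changes an overall row by 1 / 70 = 1.4 percentage points, and more in a smaller group column. The worked dates are assumptions; the mechanism depends only on the conditions listed above.

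**What to change.** Reword section 3.5.1.1 so that the steps apply in this order:

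1. Keep the reset only for an imputed start that is later than a reported end, or later than the latest date the reported end components allow. Never move a start outside its own reported components.
2. For a year-only AE end date, assign the earlier of 31 December of that year and the last contact date, with no separate last-dose branch.
3. If that imputed end is still before the reported or imputed start, move the end forward to the start.

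Step 1 keeps the safeguard for pre-treatment AEs whose start was imputed to Day 1. Steps 2 and 3 leave reported off-drug starts where they were reported. The wording should also say explicitly how complete start dates are treated.

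The cost is a few sentences of SAP text and a small programming change. No new data are needed.
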